6.10.11 Diabetic Ketoacidosis (DKA)

DKA is a serious, acute complication of diabetes and can be life-threatening. Subjects will be educated on the signs and symptoms of DKA and are required to call the study site and seek treatment should such signs or symptoms occur.

During the clinical trial period, potential DKA events will be monitored by the routine measurement of urinary ketones and assessment for signs or symptoms of acidosis at each clinic visit. Clinical presentations, such as difficulty breathing, abdominal pain, nausea, vomiting, lethargy, or a fruity smell on the breath, or laboratory values that suggest clinically-significant acidosis should be documented; treatment of DKA should be provided as appropriate.

If ongoing symptoms or signs suggest a possible DKA, the investigator should perform relevant laboratory testing while directing appropriate medical care for the subject. If DKA is suspected, regardless of the blood glucose level, the following assessments should be done immediately: physical exam and serum glucose, bicarbonate, electrolytes, and serum ketones measured STAT at a local laboratory. If ketoacidosis is likely, investigational product administration should be discontinued and immediate appropriate medical therapy, including insulin and volume repletion, should be initiated. A glucose infusion may be provided if necessary to avoid hypoglycemia during insulin therapy. Insulin treatment should continue until resolution of the ketoacidosis and stabilization of the subject's clinical condition. Investigational product administration may be resumed following stabilization of the subject's condition. Investigator should collect the data necessary for the completion of the DKA CRF.

If symptoms suggestive of DKA may have occurred but are not ongoing, the investigator should review available data in order to complete the DKA CRF. The investigator may also perform laboratory assessment using local resources if necessary for clinical care.

6.10.12 Major Adverse Cardiovascular Event (MACE)

Evaluation of MACE will be undertaken across the development program for bexagliflozin. All MACE reports should also be captured as SAEs and every effort will be made to ensure that events recorded as MACE are coded in a similar manner within the safety database. The SAE listing will also be reviewed periodically by the CEC members to identify potential MACE that may not have been reported by the site investigators. All subjects will be followed by investigators for MACE for the duration of the study even if study medication has been permanently withdrawn.

The independent CEC will receive and adjudicate the following events.

- All Deaths
- Suspected non-fatal myocardial infarction (MI)
- Suspected hospitalization for unstable angina (HUA)
- Suspected transient ischemic attack (TIA) and stroke
- Suspected hospitalization for HF (HF)
- Reported coronary revascularization procedure

The CDISC Draft Definitions for Cardiovascular and Stroke Endpoint Events in Clinical Trials will be applied by the CEC (Hicks KA, 2014).

6.10.13 Amputation

Investigators should request that subjects provide information about any amputation or related adverse event or procedures during each study visit. A case report form for adverse events that require amputations will be completed to capture the date and type of procedure, anatomic location, and causes.

Investigators are reminded to counsel appropriate foot care to avoid cuts or sores and to treat even minor cuts or sores to prevent infection and ulceration. Patients who have had a previous amputation should be closely monitored. Special attention may be appropriate for patients who are also receiving thiazide diuretics as these have been shown to increase the risk of amputation in diabetics.

6.11 Concomitant Medication Assessments

A concomitant medication is any medication that the subject has been taking prior to enrollment and that the subject is expected to continue to take for some portion of the trial, as well as any medication other than the investigational product that the subject takes during the course of the trial.

The medications or treatment for controlling hypoglycemia must be recorded as concomitant medications in the CRF. Any medication given to treat hyperglycemia is considered a rescue therapy and should be recorded in the concomitant medication log.

Changes from baseline anti-hypertensive therapy and their rationale must be recorded in the CRF.

All prescription and over-the-counter medications, including vitamins and herbal supplements, that subjects receive during the trial must be documented in the CRF. This documentation should continue until the subjects complete the study.

Concomitant medications will be coded using the World Health Organization Drug Dictionary (WHO-DD). A table of concomitant medications based on the anatomic therapeutic chemical classification (ATC) and preferred name will be produced. A listing of concomitant medications will include all medications taken by any subjects during the course of the study.

6.12 End of Treatment Procedure

The treatment period will end when (i) all randomized subjects have either completed at least 52 weeks of treatment or withdrawn from the study, and (ii) at least 134 subjects have an adjudicated MACE+ event confirmed by the CEC.

The sponsor or its designee will complete the following tasks within 7 days:

1. Notify all investigational sites, IRB/EC, and DSMB that the treatment period has ended
2. Inactivate the IWRS function for assigning investigational product

The investigators will complete the following procedures upon the notification that the treatment period has ended:

1. Contact all study subjects and schedule the end of treatment visit promptly
2. Schedule the follow up visit (FU) to occur 4 weeks after the end of treatment visit

6.13 Removal of Patients from the Trial or Discontinuation of Investigational Product Administration

The investigator must emphasize to potential subjects the importance of continued participation for the full duration of the trial during the informed consent process. Potential subjects should be informed that the trial procedures will allow additional medications to control hyperglycemia or other adverse conditions. It is also important to emphasize that missing data and missed visits could affect the entire trial. If subjects are dissatisfied with the conduct of the trial but have not withdrawn, the investigators should make an effort to address their concerns and retain them in the trial if possible. In doing so, investigators must be careful that the efforts do not cross over into coercion. Investigators should encourage a subject to remain in the study even if the investigational product administration is stopped so that safety information can be collected. If a patient is unwilling to return for study visits/assessments the investigator should ask the patient whether follow-up by telephone, through medical or other records or by contact with the patient's primary care physician is possible. The investigator should emphasize the importance for regulatory and public health/safety reasons of being able to obtain patient vital status at the end of the trial.

Participation in a clinical trial is voluntary. A subject can withdraw from the study at any time. The sponsor may terminate the study for medical or administrative reasons. An investigator may decline to participate in the conduct of the study if either the investigator or the IRB/EC determines that, based on good medical judgment, immediate cessation is appropriate for subject safety. If a decision is made to withdraw a subject from the study, no further investigational product should be administered. Even if the subject discontinues study medication, every attempt should be made to complete all required study evaluations and procedures. Reasons for all withdrawals should be recorded on the CRF. Examples of reasons for withdrawal include:

1. A protocol violation has occurred,
2. A serious or intolerable AE has occurred,
3. A clinically significant change in a laboratory parameter has occurred,
4. The sponsor terminates the study, or
5. The patient requests to be withdrawn from the study.

Subjects who do not complete the study but who have received investigational product should have a follow-up examination, including a physical examination, vital signs, ECG and clinical laboratory tests according to [Section 7](#).

Subjects who withdraw from the study will not be replaced.

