9.6.3 Safety Endpoint

The safety endpoint of the program-wide meta-analysis is the hazard ratio for the time to first occurrence of adjudicated MACE+ which is defined as the composite of CV death, non-fatal MI, non-fatal stroke and hospitalization for unstable angina. All these events will be adjudicated by an independent CEC, blinded to treatment assignments. A Cox proportional hazards model with treatment and randomization stratification factors as the covariates will

be used to estimate the hazard ratio of the composite endpoint and its two-sided 95 % confidence interval comparing bexagliflozin to placebo. The analysis set is the Safety Analysis Set. Subjects who withdraw from the study early and subjects who did not prematurely terminate but who did not experience a MACE+ event by the end of the study will be censored at the last known follow-up.

As a sensitivity analysis, the incidence of MACE+ will be compared between treatments following multiple-imputation of the MACE+ endpoint. The methodology for sensitivity analyses of time-to-event data to be used will be that described in *Zhao, Yue, et al (Zhao et al., 2014)*. The dropout patterns will be assessed by Kaplan-Meier plots if applicable to assess whether they differ between treatment groups.

In addition, a sensitivity analysis will be conducted separately for subjects who enrolled prior to inclusion criteria modification and subjects who enrolled post inclusion criteria modification.

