10.10 Protocol Violations/Deviations

Protocol violations include deviations from the inclusion and exclusion criteria, concomitant medication restrictions, and any other protocol requirement that results in a significant added risk to the patient or has an impact on the quality of the data collected or the outcome of the study. A deviation occurs when there is non-adherence to study procedures or schedules, as specified by the protocol, which does not involve inclusion/exclusion criteria or the primary endpoint and which does not place the patient at any added risk or affect the data quality or study outcome. Examples of deviations may include common out-of-window visits, a missed procedure, etc. Protocol violations will be reported in the final clinical study report, whereas protocol deviations may be mentioned but are not required to be reported.

It is important to conduct the study according to the protocol. Protocol deviation waivers will not be prospectively granted by the sponsor. If minor protocol deviations occur, the investigator must decide the most appropriate way to proceed with study activities and should consult the study representative for assistance. If major protocol deviations occur, the sponsor's medical monitor must be notified immediately so that a decision about whether to keep the subject in the study can be made.

Only when an emergency occurs that requires a departure from the protocol for an individual subject can there be a departure without the sponsor's pre-approval. The nature and reasons for the protocol deviation will be recorded in the subject's CRF, and the principal investigator must notify the Sponsor.

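### Protocol 6.13 does not separate stopping investigational product from leaving the study, which conflicts with the rule that all subjects are followed for MACE to study end

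*Combined protocol and SAP*

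**What the plan says.** Protocol 6.10.12 sets the follow-up rule: "All subjects will be followed by investigators for MACE for the duration of the study even if study medication has been permanently withdrawn".

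Protocol 6.13, whose title covers both removal from the trial and discontinuation of investigational product, first encourages retention. It then treats study exit as something that may be decided about a subject: "If a decision is made to withdraw a subject from the study, no further investigational product should be administered". Its example reasons include "A protocol violation has occurred", "A serious or intolerable AE has occurred" and "A clinically significant change in a laboratory parameter has occurred". Two further items are sponsor termination and "The patient requests to be withdrawn from the study".

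Protocol 10.10 requires notice to the medical monitor after a major deviation, "so that a decision about whether to keep the subject in the study can be made".

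For the MACE+ analysis, Protocol 9.6.3 states that subjects who leave early "will be censored at the last known follow-up".

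**The concern.** If all subjects are followed for MACE whether or not they take drug, an adverse event, a laboratory change or a deviation can be a reason to stop drug but should not be a reason to stop observing. Section 6.13 mixes the two. Because the patient's own request has its own item, the first three items cannot be read as shorthand for withdrawn consent.

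Two analyses are exposed.

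- **MACE+.** Exit after a serious event or a laboratory change is plausibly related to later cardiovascular risk and may differ by arm. Censoring at exit then carries information into the hazard ratio that goes to the meta-analysis. A heart failure hospitalization shows the route: it would ordinarily be serious under Protocol 6.10.1, but it is not a MACE+ component, so an exit at that point comes before any later MI, stroke or CV death is counted.
- **HbA1c at week 24.** SAP 8.1.1 imputes missing values for subjects who stopped treatment from subjects in the same arm who stopped but were still measured. It runs this analysis only if at least 5 subjects per arm completed the week 24 visit after stopping. If leaving the study coincides with stopping drug, those are the values lost.

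**Working it through.** **1. The provisions side by side**

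| Place | Situation | Follow-up |
|---|---|---|
| Protocol 6.10.12 | Drug permanently stopped | MACE follow-up of all subjects to study end |
| Protocol 6.13, retention text | Drug stopped, or subject unwilling to attend | Encourage staying; telephone, records or primary-care contact; vital status |
| Protocol 6.13, withdrawal text | Decision to withdraw from the study; example reasons include violation, AE, laboratory change | For non-completers, names only a follow-up examination |
| Protocol 7.5 | Drug stopped, subject willing to stay | Safety data continue to be collected |
| Protocol 7.6 | Consent withdrawn | Follow-up examination; sponsor also told of subjects who have been withdrawn |
| Protocol 9.5.2 | Dropouts | Points to 6.13 for the discontinuation criteria |
| Protocol 10.10 | Major deviation | Subject may or may not be kept in the study |
| SAP 9.3.2 | TEAE tables | Study discontinuation tabulated apart from treatment discontinuation |

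Study exit that is not the subject's own choice is therefore a route that several sections recognize. No sentence says which provision governs when 6.13 and 6.10.12 point different ways.

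**2. Effect on the event count**

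Inputs from Protocol 9.2: N = 1650; reference hazard h = 0.00308 per month; true hazard ratio 1.00; annual withdrawal 6.5%, so d = −ln(1 − 0.065)/12 = 0.00560 per month; enrollment 1 year; maximum follow-up 3 years. Uniform enrollment over 1 year with a 3-year maximum implies follow-up t between 24 and 36 months.

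Expected events = 1650 × h/(h+d) × mean over t of [1 − exp(−(h+d)t)]

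- h/(h+d) = 0.00308/0.00868 = 0.355
- mean of the bracket over 24 to 36 months = 0.229
- 1650 × 0.355 × 0.229 = 134.0 (computed without rounding)

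This reproduces the plan's 134. Taking the stated 1-year minimum follow-up literally gives 109.

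Varying only the withdrawal rate:

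| Annual withdrawal | Events at 3 years | Study length for 134 events |
|---|---|---|
| 0% | 145.5 | 2.79 years |
| 6.5% (plan) | 134.0 | 3.00 years |
| 10% (assumed) | 128.0 | 3.14 years |
| 13% (assumed) | 123.0 | 3.29 years |

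Removing every withdrawal, for whatever reason, adds 145.5 − 134.0 = 11.5 events by year 3, or saves 3.00 − 2.79 = 0.21 years (about 2.5 months). The part due to the three disputed reasons lies between zero and that figure. The formula gives withdrawn subjects average risk; if they are at higher risk, more events are lost per withdrawal.

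**3. Illustration of bias (all loss rates assumed)**

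If a fraction a of would-be events is lost on active and p on placebo, and time at risk barely changes, the observed hazard ratio is roughly the true one × (1 − a)/(1 − p).

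- a = p = 5%: factor 1.00, no bias.
- a = 10%, p = 5%: 0.90/0.95 = 0.947; a true 1.8 appears as 1.8 × 0.947 = 1.71. With 134 events, the share on active is 2 × 1.705/(1 + 2 × 1.705) = 0.773. The one-sided error is Φ(ln(1/0.947) × √(134 × 0.773 × 0.227) − 1.96) = Φ(0.262 − 1.96) = 4.5%, against a nominal 2.5%.
- a = 5%, p = 10%: 0.95/0.90 = 1.056; the bias runs the other way, and a true 1.8 appears as 1.90.

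This treats the 134 events as if analyzed alone. The formal test belongs to the meta-analysis.

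**The case against.** The strongest reply is that the list only illustrates reasons to be recorded on the CRF. It compels nothing, and the sentence before it asks sites to do all they can to finish assessments after drug stops. Protocol 7.5 provides a procedure for off-drug follow-up. SAP 7.1 seeks vital status after study exit, and SAP 8.1.1 repeats the commitment to retention. Protocol 9.6.3 adds a multiple-imputation sensitivity analysis for MACE+, using a method whose reference title names possibly informative censoring, and dropout plots by arm. The 6.5% withdrawal rate is already in the event projection.

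Most of this stands, and it lowers the risk. It does not close the gap. The retention sentences address subjects who stop drug or are unwilling to attend; they do not address a willing subject whom the site or sponsor withdraws. Vital status recovers deaths but not a non-fatal MI, stroke or unstable angina admission. Imputation does not replace observation.

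Three stronger readings are tempting and are not supported:

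- **That a site may follow 6.13 to the letter and properly end follow-up after a serious event.** Doing so would breach 6.10.12 and go against 6.13's own retention text. The fault is a conflict between provisions, not a permission.
- **That the trial would fall short of its events or lose power.** Treatment continues until at least 134 subjects have an adjudicated MACE+.
- **That the loss can be projected from heart failure admissions.** Protocol Table 2 implies 0.017 × 1250 + 0.102 × 400 = 62 in two years, but no document gives the share that would lead to withdrawal. The higher CV death rate in Protocol 3.3.3 (0.0365 against 0.0115 per subject-year, a ratio of 3.2) applies to subjects with a heart failure history, who account for only 41 of the 62.

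**Conclusion.** The conflict is real and should be resolved. Protocol 6.13 and 10.10 leave open ending a subject's participation for reasons that 6.10.12 does not accept as ending MACE follow-up, and such exits are then censored. The consequence is possible informative censoring of MACE+, a somewhat longer trial, and fewer off-treatment week-24 HbA1c values for the SAP's primary imputation. If the threshold of 5 per arm is missed, SAP 8.1.1 falls back to MMRM on available data.

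The size cannot be derived because withdrawals are not split by reason. If withdrawal is unrelated to risk, the event effect is bounded by about 11 events or 2.5 months. The direction and size of any bias depend on differences between arms for which the documents give no figures; the shift from 1.8 to 1.71 is an assumed scenario, not an estimate.

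**What to change.** Reconcile Protocol 6.13 and 10.10 with 6.10.12 and 7.5:

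- In 6.13, treat discontinuation of investigational product and withdrawal from the study as two separate actions, each with its own recorded reason.
- State that an adverse event, a laboratory change or a protocol deviation does not by itself end follow-up. Visits, week-24 HbA1c, AE, MACE and vital-status collection continue unless consent is withdrawn or the study is terminated.
- In 10.10, make the decision after a major deviation one about handling the deviation, with its effect on the efficacy analysis dealt with through the per-protocol set (SAP 5.5).
- Reconcile the pregnancy text in 6.10.4, which withdraws the subject from the trial, with the revised wording.

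The rules on when drug is stopped need no change. The cost is amendment wording, site retraining and some off-drug contacts, which 6.10.12 already requires.

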6.14 Appropriateness of Measurements

The percentage of HbA1c is a widely used measure of chronic glycemia, reflecting average blood glucose levels over a 2- to 3-month period of time. It is an accepted surrogate marker for risk of microvascular complications and is widely used as a measurement for the

adequacy of glycemic management. Other study procedures and measurements in this protocol are widely used and generally recognized as reliable, accurate, and relevant for subjects with T2DM.

7 STUDY ACTIVITIES

The study activities at each clinic visit listed below are presented in [Appendix 1](#). The required laboratory tests scheduled at each visit are listed in [Appendix 2](#). Detailed study procedures are described in [Section 6](#).

A visit window of ± 3 days is allowed for all visits except visit V3. Visit 3 is the day of randomization and the basis for the visit window.

7.1 Screening Visit V1 (up to 3 weeks before run-in period)

The screening can be performed from 3 weeks to 3 days before the start of the run-in period for subjects. At the screening visit the staff at the investigational site will:

- Explain the content of the informed consent materials to the subject and collect signed informed consent
- Evaluate inclusion and exclusion criteria based on the information collected at the screening visit. Verify compliant fasting status as described in [Section 6.7.2.1](#).
- Obtain medical history and demographic information
- Perform a brief physical examination
- Measure vital signs, including blood pressures and heart rate
- Measure body weight and height
- Perform a 12-lead ECG measurement
- Draw serum sample for NT-proBNP evaluation within 1 h of the ECG measurement from Group 2 subjects with undocumented left ventricular ejection fraction (LVEF) or LVEF > 40%
- Draw blood if a minimum 10-h fast has been completed by the subject as described in [Section 6.7.2.1](#). The specific laboratory tests scheduled for this visit are listed in [Appendix 2](#).
- Collect clean-catch, mid-stream urine sample for urinalysis, and pregnancy test for all females

7.2 Run-in Period

7.2.1 Visit V2 (two weeks prior to randomization)

- Counsel subject on appropriate diet and exercise
- Dispense glucometer and instruct subject in SMBG determination and recording
- Measure body weight
- Dispense run-in kit for run-in period
- Assess pre-treatment signs and symptoms and potential DKA and record pre-treatment concomitant medications

7.3 Treatment Period

At the end of the run-in period, subjects who have successfully completed run-in period and continue to meet inclusion/exclusion criteria will be randomized and enter the treatment period. At the following visits staff at the investigational site will:

7.3.1 Visit V3 (day 1 of week 1)

- Confirm inclusion/exclusion criteria for eligibility and review run-in drug compliance
- Perform a complete physical examination
- Review glycemic control and SMBG. Dispense glycemic control diary.
- Measure vital signs, including blood pressures and heart rate
- Measure body weight
- Perform 12-lead ECG
- Draw blood from subjects who have completed a compliant fast as described in [Section 6.7.2.1](#). The specific laboratory tests scheduled for this visit are listed in [Appendix 2](#)
- Collect a clean-catch, mid-stream urine sample for urinalysis and UPT for women of child bearing potential.
- Dispense investigational product based on randomization
- Assess pre-treatment signs and symptoms and potential DKA and record pre-treatment concomitant medications.

